Advarra IRB Approval Date : August 27th 2018

NCT03690375

ID: Purpura001

[name]

Documents Enlcosed:

- 1. Statistical Analysis Plan
- 2. Protocol

STATISTICAL ANALYSIS PLAN

Primary Endpoint

$$H_0: \mu_C = 0$$
; $H_1: \mu_C > 0$

- > The null hypothesis is the absolute mean difference in the change from baseline to 30 days after the last treatment on the treatment arm as compared to the non-treatment arm is zero.
- The alternative hypothesis is the absolute mean change from baseline to 30 days after the last treatment on the treatment arm as compared to the non-treatment arm is greater than zero.
- 1. Let μ_C represent the absolute mean difference between the treated arm as compared to the non-treated arm in the difference in the number of ecchymoses from baseline to 30 days after the last treatment.
- 2. Let μ_C represent the absolute mean difference between the treated arm as compared to the non-treated arm in the difference in the size of ecchymoses from baseline to 30 days after the last treatment.

A Paired t-test will be used to analyze the primary endpoint. The results of the statistical analysis will be presented as an odds ratio with 95% Confidence intervals. A Shapiro-Wilk Test will be used to assess the normality of data.

PROTOCOL

A Prospective, Randomized, Split-Arm Clinical Study Investigating the Efficacy and Safety of Sciton's Broad Band for the Treatment and Prevention of Senile Purpura

Pilot Study

[name] M.D.

A Prospective, Randomized, Split-Arm Clinical Study Investigating the Efficacy and Safety of Sciton's Broad Band for the Treatment and Prevention of Senile Purpura

Principal Investigator: [name] MD

[name]

[name]

[contact]

[contact]

Email Address: [contact]

Statistician: [name]

[contact]

Email Address: [contact]

Study Cooridnator: [name]

Study Evaluator: [name]

[name]

[name]

[contact]

[contact]

STATEMENT OF COMPLIANCE

Signed:

The trial will be conducted in accordance with the ICH E6 and the Code of Federal Regulations on the Protection of Human Subjects (45 CFR Part 46). The Principal Investigator will assure that no deviation from, or changes to the protocol will take place, except where necessary to eliminate an immediate hazard(s) to the trial participants. All personnel involved in the conduct of this study have completed Human Subjects Protection Training.

I agree to ensure that all staff members involved in the conduct of this study are informed about their obligations in meeting the above commitments.

Principal Investigator: [name]

_Date: ______ Signature

Title:

A Prospective, Randomized, Split-Arm Clinical Study Investigating the Efficacy and Safety of Sciton's Broad Band for the Treatment and Prevention of Senile Purpura

Précis:

There will be ten subjects, 5 older subjects over 65 years of age with at least one ecchymotic lesion on each arm measuring at least one cm, and 5 subjects under 35 years of age. All subjects will be randomized to undergo 4 Sciton Broad Band Light (BBL) treatments on either their left or right arm one week apart. Subjects will fill out questionnaires, have pictures of their lower arms taken, and will be graded and measured by evaluators regarding the number and size of their ecchymoses as well as side effects such as blistering, pain, erythema, and swelling. One day after their 4th treatment, subjects will have biopsies done to be analyzed for changes in histology and gene expression. The subjects will follow up at 30 days after their last treatments for final pictures of their lower arms and evaluations.

Objectives:

Primary Objectives: To assess the efficacy of BBL in improving the appearance of senile purpura

Important Secondary Objectives:

- 1. To assess the safety of a new BBL protocol for treating and preventing senile purpura
- 2. To assess the efficacy of BBL in reducing skin tears
- 3. To assess the efficacy of BBL to improve the histology of the skin
- 4. To assess the efficacy of BBL to increase epidermal thickness
- 5. To assess the efficacy of BBL to change gene expression

Endpoint

Primary Endpoints:

- Mean absolute difference in the BBL treated arms as compared to the non-treated arms of those with senile purpura in the total square area of purpuric lesions from the first treatment to 30 days after the last treatment
- Mean absolute difference in the BBL treated arms as compared to the non-treated arms of those with senile purpura in the number of purpuric lesions from the first treatment to 30 days after the last treatment

Important Secondary Endpoints:

1. Measurement of pain, swelling, blistering, erythema, and all sideeffects immediately after each procedure, as well as 24 hours, 48 hours, and 7 days after the procedure.

- 2. Mean absolute difference in the number of skin tears at baseline and 30 days after the last treatment
- 3. The changes in collagen and elastin between untreated and treated skin
- 4. Mean absolute difference in the change in epidermal thickness between treated and untreated skin
- 5. Changes in gene expression between treated and untreated skin

Population: Sample size 10

Male and female adults over the age of 21 living in Palm Beach

County Florida.

Number of Sites 1

Study Agent: Sciton's BBL

Study Duration: 51 days

SCHEMATIC OF STUDY DESIGN

Day -30 to 0 Screening

- •Total n=10
- Obtain informed consent
- Screen potential subjects by inclusion and exclusion criteria (Eligibility Questionnaire)

Day 0: Randomization

•Subjects randomized to have BBL on either their left or right

Day 0: Baseline assessments/ Study Intervention

• Baseline Assessments:

Pre-procedure pictures of patient's lower arms taken with a Digital Camera

Baseline assessment and measurement by evaluator

Baseline Medical History and Medication questionnaires completed by all subjects

• Study Intervention #1:

Sciton's BBL done according to purpura protocol on one arm according to randomized assignment

• Post-Procedure Assessments:

Post-procedure questionnaires filled out by all subjects

Day 1: Follow-up assessments

• At Home Follow-up Assessments Questionnaire Regarding Side-Effects

Day 2: Follow-up assessments

• At Home Follow-up Assessments Questionnaire Regarding Side-Effects

Day 7 +/- 2 Days: Follow-up assessments / Study Intervention

Follow-up assessments:

Evaluator assessment and measurement

Pictures taken of subject's lower arms

Subject follow up questionnaires filled out by all subjects

• Study Intervention #2:

Sciton's BBL done a second time on the assigned arm according to protocol settings

• Post-Procedure Assessments:

Day 14 +/- 2 Days: Follow-up assessments / Study Intervention

• Follow-up assessments:

Evaluator assessment and measurement Pictures taken of subject's lower arms

Subject follow up questionnaires filled out by all subjects

• Study Intervention #3:

Sciton's BBL done a third time on the assigned arm according to protocol settings

• Post-Procedure Assessments:

Post-procedure questionnaires filled out by all subjects immediately after treatment

Day 21 +/- 2 Days: Follow-up assessments / Study Intervention

• Follow-up assessments:

Evaluator assessment and measurement

Pictures taken of subject's lower arms

Subject follow up questionnaires filled out by all subjects

• Study Intervention #4:

Sciton's BBL done a fourth time on the assigned arm according to protocol settings

• Post-Procedure Assessments:

Post-procedure questionnaires filled out by all subjects immediately after treatment

Day 22 +/- 2 Days: Follow-up assessment via skin biopsy

• A 4mm punch biopsy will be done on both the treated and untreated arm approximately 4cm below the crease in the antecubital fossa

Day 51 +/- 2 Days: Follow-up assessment

Follow-up assessments:

Evaluator assessment and measurement

Pictures taken of subject's lower arms

Subjects follow up questionnaires filled out by all subjects

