Multiple studies have shown the efficacy of topical Retinol and Tretinoin in increasing epidermal thickness and one study in particular in the Journal of Cosmetic Dermatology in 2016 showed not only an increased thickness in the epidermis but also up-regulated genes for Collagen Type 1 (COL1A1) and Collagen Type 3 (COL3A1) with corresponding increases in procollagen 1 and procollagen 3 protein expression (7).

A very small study (N=6) on the effectiveness of human epidermal growth factor for the treatment of actinic purpura when applied twice daily for six weeks showed an increase epidermal thickness on ultrasound and the mean number of lesions decreased from 15 to 2.3 (8).

More recently in 2017, Ceilley published his experience with DerMend in the Journal of Cllinical and Aesthetic Dermatology, reviewing why he thought a topical preparation with Retinol, Alpha hydroxyl acids, Arnica oil, Ceramindes, Niacinamide, and Phytonadione would be an optimal treatment for this condition (3).

The current literature supports the ability of IPL to induce collagen neogenesis. Studies on mice showed that IPL treatments significantly increased the number of collagen and elastic fibers within the dermis and improved the parallel distribution of collagen fibers in relation to the epidermis. These results were only evident after three IPL treatments spaced 2 weeks apart and not after just one or two treatments (5). In a study with rats, IPL increased dermal collagen fibers and collagen fiber diameter after 3 weeks (9) and in another study on rats, IPL increased dermal thickness, density of collagen, the hydroxyproline content, and the expression of III procollagen mRNA (18). In one study in humans, 5 patients showed histological evidence of new collagen formation 6 months after four IPL treatments (19). The current literature not only supports the ability of IPL to induce collagen neogenesis but also microneedling and microneedling with radiofrequency. One study showed microneedling resulted in greater skin and dermal thickness than IPL and increased expression of Type 1 collagen and total collagen content (20).

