3 STUDY DESIGN, OBJECTIVES, AND ENDPOINTS

3.1 DESCRIPTION OF THE STUDY DESIGN

- A Prospective, Randomized, Split-Arm Clinical Study
- Single Center
- Study agent: Sciton's BBL
- Study Interventions: BBL Treatment on Day 0, Day 7, and Day 21
- Evaluations on Day 0, Day 7, Day 14, Day 21, Day 22, Day 51.

This will be a prospective, split-arm clinical study in which 5 subjects will be randomized to which arm will be treated with Sciton's BBL.

All subjects will have their arms shaved prior to the procedure and cleaned thoroughly with alcohol. After the procedure a zinc-based sunscreen will be applied to both arms.

Before each of the four treatments and 30 days after the last treatment, the subjects' number and square area of ecchymoses will be measured by an evaluator. Side effects will be measured on Day 0, 1, 2, 7, 14, 21, 22 and 51. Digital photography of subject's arms will be done on day 0, 7, 14, 21, and 51.

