3.2.2 PRIMARY ENDPOINT

➤ Primary Endpoint: Mean absolute difference between the treated and non-treated arms in the change of total square area and number of ecchymoses from baseline to 30 days after the last treatment.

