4 STUDY ENROLLMENT AND WITHDRAWAL

4.1 PARTICIPANT INCLUSION CRITERIA

In order to be eligible to participate in this study, an individual must meet all of the following criteria:

- Provision of signed and dated informed consent form
- Stated willingness to comply with all study procedures and availability for the duration of the study
- Male or female, aged >22
- In good general health as evidenced by medical history
- Ecchymosis greater than 1cm on each arm

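### The primary paired t-test uses raw lesion numbers and areas in 5 purpura subjects with no upper limit on burden; if burden varies widely it can miss a consistent proportional effect, and a prespecified square-root scale would help at a small cost that the SAP should state

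*Combined protocol and SAP*

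**What the plan says.** The SAP (Primary Endpoint) and section 8.1 carry the same text: "A Paired t-test will be used to analyze the primary endpoint". Section 3.2.2 defines the endpoint as "Mean absolute difference between the treated and non-treated arms in the change of total square area and number of ecchymoses", which is a difference on the raw scale. No transformation, baseline adjustment or alternative test is given. The next sentences promise an odds ratio with a 95% interval and add "A Shapiro-Wilk Test will be used to assess the normality of data", without saying what follows from that check.

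The précis restricts the primary endpoints to the arms "of those with senile purpura in the total square area of purpuric lesions" (and, likewise, their number). It describes the purpura group as "5 older subjects over 65 years of age with at least one ecchymotic lesion on each arm measuring at least one cm". Section 3.1 also refers to five: "5 subjects will be randomized to which arm will be treated". Section 4.1 sets a lower limit on burden, "Ecchymosis greater than 1cm on each arm", and no upper one. Section 8.4 gives no sample-size calculation because this is a pilot. The only lesion count in the documents is in section 2.1, for a cited six-subject study of a topical growth factor, where "the mean number of lesions decreased from 15 to 2.3".

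**The concern.** Lesion counts and summed areas usually vary more where there are more lesions, and an arm cannot lose more lesions than it has. If BBL clears a similar share of purpura in each subject, the raw differences are proportional to burden. The spread in severity between subjects then becomes the SD that the effect is judged against. With five differences, one heavily affected subject can raise that SD enough for the test to fail although every subject improved equally in relative terms.

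The pilot could then report no effect, with an interval that includes zero, because its subjects differed in severity. The scale has to be fixed beforehand, since choosing it after seeing five differences would not be credible.

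**Working it through.** **Inputs from the documents.** Five pairs and 4 degrees of freedom (précis); raw scale (section 3.2.2); no upper limit on burden (section 4.1). Alpha is not stated. The alternative is written as one-sided and the interval as 95%, so results below use a two-sided 5% level or, equivalently for benefit, a one-sided 2.5% level (critical t = 2.776). The documents give no power, SD or BBL effect to reproduce. Everything below about burden and effect is assumed.

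**Step 1: exact proportional effect, no noise.** Suppose subject i has baseline burden B on both arms, the control arm is unchanged and the treated arm falls by a fraction r.

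- The raw paired difference is rB, so t = mean / (SD/√5) = √5 / CV(B). The size of r cancels.
- Significance needs CV(B) < 2.236/2.776 = 0.81.
- On the square-root scale the difference is √B × (1 − √(1 − r)), so t = √5 / CV(√B), and √B has a smaller CV.

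**Step 2: worked example.** Areas of 2, 3, 4, 6 and 40 cm² on each arm, r = 0.60.

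- Raw differences are 1.2, 1.8, 2.4, 3.6 and 24.0: mean 6.6, SD 9.77, SE 9.77/√5 = 4.37. t = 6.6/4.37 = 1.51, p = 0.21, 95% CI 6.6 ± 2.776 × 4.37 = −5.5 to 18.7 cm². The largest subject supplies 24/33 = 73% of the summed effect.
- Square-root differences have mean 1.02 and SD 0.74: t = 3.09, p = 0.037.

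The gain comes from a smaller SD relative to the mean (9.77/6.6 = 1.48 raw, 0.74/1.02 = 0.73 square root). The largest subject still supplies most of the sum of squares on both scales: (24 − 6.6)²/(4 × 9.77²) = 79% raw and about 77% square root.

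Other assumed burdens with the same 60% fall:

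- 3, 5, 8, 12, 40: raw p = 0.115, square root p = 0.015.
- 2, 3, 4, 6, 12: raw p = 0.038, already significant.
- 3, 4, 5, 6, 7: raw p = 0.002.

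**Step 3: simulation with sampling noise.** Five pairs; lognormal subject lesion rates (log-SD 0.7); arm-level log-SD 0.2; Poisson counts with at least one lesion per arm at Day 0; lognormal lesion areas (median 1.5 cm², log-SD 0.8). Each cell has 40,000 trials at one-sided 2.5%. The 85% fall is (15 − 2.3)/15 = 84.7% from the cited study.

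| Lesions per arm, fall | Number: raw v square root | Area: raw v square root |
|---|---|---|
| 8, 85% | 36% v 64% | 24% v 54% |
| 15, 85% | 48% v 82% | 35% v 71% |
| 8, 50% | 16% v 25% | 11% v 18% |

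Over the full grid (means 4 to 15, log-SD 0.3 to 1.0), type I error was 1.6% to 2.6% raw and 2.3% to 2.7% on the square root.

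**Step 4: dependence on spread.** Separate runs for counts (median 8, 80% fall, two-sided 5%) gave, raw v square root: 57% v 74% with no spread in burden, 51% v 73% at log-SD 0.4, 39% v 70% at 0.7 and 27% v 64% at 1.0. For areas with a median of 15, a 50% fall and no spread, the figures are 15% v 19%.

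**Step 5: additive effect.** With a fixed number of lesions removed and noise that does not grow with burden (median 15, 4 removed, noise SD 1.5), the square root loses: 60% v 58% at log-SD 0.4, 59% v 50% at 0.7 and 56% v 42% at 1.0. The largest loss found in these runs was 65% v 47% (3 removed, noise SD 1, log-SD 1.0). With a fixed number removed but Poisson noise (15 lesions, 6 removed, log-SD 0.7), the square root wins: number 30% v 41%, area 18% v 30%.

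**Step 6: Shapiro-Wilk.** It can reject in an extreme sample (p = 0.032 for the raw differences from 3, 5, 8, 12, 40). In simulation it rejected in about 11% (log-SD 0.7) to 18% (log-SD 1.0) of trials for counts, and 4% to 15% for areas.

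**The case against.** The strongest objection is that the square root changes what is tested. The endpoint and hypotheses concern the mean difference in lesions and area. The square root gives less weight to the most affected subjects, which is partly a clinical choice, and does not convert back to a mean difference. The two scales can even differ in sign. Treated-arm baselines of 2, 2, 3, 4 and 30 going to 4, 4, 5, 6 and 20 give a mean reduction of +0.4 lesions, since (−2 − 2 − 2 − 2 + 10)/5 = 0.4, but −0.20 on the √(number + 3/8) scale. This stands, and the SAP should say so. It needs effects in opposite directions between subjects.

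Second, the simulations mostly use Poisson counts, the case that suits a square root, and Step 5 shows a reversal. That also stands, but noise that stays constant as burden rises is not what one expects of lesion counts and summed areas.

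Third, a pilot that claims no power could keep the raw test and add a sensitivity analysis. That is defensible. A sign-flip test is a weak substitute as primary, however: with five pairs its smallest p is 1/32 = 0.031 one-sided and 2/32 = 0.0625 two-sided.

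Fourth, the cited 15 lesions are not stated to be per arm and come from another treatment, so they only illustrate a scale.

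**Conclusion.** The concern holds conditionally. The raw-scale test, the five subjects, the missing upper limit on burden and the normality check without a consequence are in the documents. If burden varies widely, variability grows with burden and BBL acts roughly proportionally, the planned test can miss a consistent effect. At log-SD 0.7 with an 85% fall, the square root adds about 28 to 36 points of power.

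A reader might infer four stronger things that the documents do not support:

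- That the change is free. It alters the tested quantity and the weight given to severe subjects.
- That it restores adequate power. Most square-root figures in Step 3 stay below 80%, and with a 50% fall they are 18% and 25%.
- That the raw test will fail. No SD, burden distribution or BBL effect is given, and with similar burdens it can already succeed.
- That the raw t-test is invalid. Its simulated type I error is at or below about nominal, so the problem is lost sensitivity.

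This is a change the sponsor should make, with medium confidence about its size.

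**What to change.** In the SAP and section 8.1, before unblinding:

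- State that the paired t-test is done in the senile purpura subjects on the treated-minus-untreated difference in change from baseline of √(total area) and of √(number + 3/8). Neither needs a special rule for an arm that clears to zero.
- Report the raw mean differences, in cm² and in lesions, with 95% CIs as the effect estimates, in place of the odds ratio.
- Show all five paired values.
- State that Shapiro-Wilk will not be used to choose the test.
- State the cost: the test no longer addresses the raw mean difference directly, gives less weight to the most affected subjects, and may disagree with the raw estimate, even in sign, if effects differ in direction between subjects. Any such disagreement will be reported.
- State alpha and sidedness, and reconcile the group size. Section 4.1 requires ecchymosis of every participant, while the précis sets no lesion requirement for the five younger subjects.

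This changes wording only, with no new subjects, visits or measurements.

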2.1 BACKGROUND INFORMATION

Senile Purpura is a benign common condition characterized by recurrent formation of ecchymosis on the extensor surfaces of forearms and hands following minor trauma. Other names of this condition are Bateman purpura, named after British dermatologist Thomas Bateman, who first described it in 1818, and actinic purpura, because of its association with sun damage (1).

More recently in 2007, Kaya and Saurat coined the term dermatoporosis to describe the chronic cutaneous fragility of aging skin. Dermatoporosis features include thinning atrophic skin, purpura, skin lacerations and delayed healing (2).

This condition affects over 10% of those aged over 65 years old and is equally common in males and females. Risk factors are known to include the use of oral or topical corticosteroids and anti-coagulants (3).

With age and sun damage, the dermis becomes thin. As a result, this condition results from superficial vessels tearing even with negligible trauma. The subsequent extravasation of blood into the surrounding dermis results in the development of ecchymosis. Histologically, the epidermis is thinned and the dermis demonstrates significantly reduced amounts of collagen replaced by abnormal elastic fibers, as well as extravasated red blood cells (4).

Intense pulsed light (IPL) is non-coherent, non-collimated, polychromatic light energy. IPL emits different wavelengths that target specific chromophores. This makes IPL a versatile therapy with many applications, from the treatment of pigmented or vascular lesions to hair removal and skin rejuvenation. Its large spot size ensures a high skin coverage rate and ease of use over large areas. The treatment has very little downtime given its non-ablative nature which makes it an attractive option. In many cases, IPL is similar to laser therapy in effectiveness, convenience, and safety and together with its versatility will lead to an expanded range of applications and possibilities in the future.

Relevant Clinical Research

Published studies on treatments for senile or actinic purpura or dermatoporosis are very limited. In one small double blinded study (N=14) published in 1995 in The Archives of Dermatology, they showed twice daily treatment with retinoic acid cream resulted in significant reduction in Bateman's actinic purpura after two weeks, however there were no significant differences after that time (6).

Multiple studies have shown the efficacy of topical Retinol and Tretinoin in increasing epidermal thickness and one study in particular in the Journal of Cosmetic Dermatology in 2016 showed not only an increased thickness in the epidermis but also up-regulated genes for Collagen Type 1 (COL1A1) and Collagen Type 3 (COL3A1) with corresponding increases in procollagen 1 and procollagen 3 protein expression (7).

A very small study (N=6) on the effectiveness of human epidermal growth factor for the treatment of actinic purpura when applied twice daily for six weeks showed an increase epidermal thickness on ultrasound and the mean number of lesions decreased from 15 to 2.3 (8).

More recently in 2017, Ceilley published his experience with DerMend in the Journal of Cllinical and Aesthetic Dermatology, reviewing why he thought a topical preparation with Retinol, Alpha hydroxyl acids, Arnica oil, Ceramindes, Niacinamide, and Phytonadione would be an optimal treatment for this condition (3).

The current literature supports the ability of IPL to induce collagen neogenesis. Studies on mice showed that IPL treatments significantly increased the number of collagen and elastic fibers within the dermis and improved the parallel distribution of collagen fibers in relation to the epidermis. These results were only evident after three IPL treatments spaced 2 weeks apart and not after just one or two treatments (5). In a study with rats, IPL increased dermal collagen fibers and collagen fiber diameter after 3 weeks (9) and in another study on rats, IPL increased dermal thickness, density of collagen, the hydroxyproline content, and the expression of III procollagen mRNA (18). In one study in humans, 5 patients showed histological evidence of new collagen formation 6 months after four IPL treatments (19). The current literature not only supports the ability of IPL to induce collagen neogenesis but also microneedling and microneedling with radiofrequency. One study showed microneedling resulted in greater skin and dermal thickness than IPL and increased expression of Type 1 collagen and total collagen content (20).

In Patrick Bitter's pilot study published in 2015 in the Journal of Cosmetic Dermatology, they used 3'-end sequencing for expression quantification ("3-seq") to discover the gene expression associated with human skin aging and the impact of broadband light (BBL) treatment. In the study skin aging was associated with a significantly altered expression of 2,265 coding and noncoding RNAs, of which 1,293 became "rejuvenated" after BBL treatment (more similar to expression levels in youthful skin). Rejuvenated genes (RGs) included several known key regulators of organismal longevity (16). Hence, according to this study, BBL treatment appears to be able to restore gene expression pattern of photo aged and intrinsically aged human skin to resemble young skin and therefore may be an ideal treatment option for senile or actinic purpura.

In addition, though most cosmetic surgeons and injectors have seen firsthand the improvement of post procedural bruising with both pulse dye lasers or intense pulse light lasers, there are limited published studies on this topic. One study published in the Archives of Plastic Surgery in 2009 showed pulsed-dye laser was effective for treating ecchymoses after facial cosmetic procedures and resulted in a 63% mean improvement in ecchymosis scores within 48 to 72 hours (14), however there are no published studies to date using IPL.

